6.4 Treatment of Study Drug Overdose

For this study, accidental or intentional oral ingestion of drug product will be considered an overdose. Ingestion of a 30-gram tube of tapinarof cream, 1% would result in an oral dose of 300 mg.

The Sponsor does not recommend specific treatment for an overdose; however, in the event of an overdose, the Investigator (or treating physician) should do the following:

- Contact Medical Monitor to discuss the event
- Closely monitor the subject for AEs/SAEs and laboratory abnormalities
- Provide general symptomatic treatment as necessary
- Document the quantity of the excess dose as well as the duration of the overdosing.
- If the Medical Monitor requests a plasma sample for PK analysis, then a blood sample for PK should be obtained within 2 days from the date of the last dose of study drug.

Decisions regarding dose interruptions or modifications following an overdose will be made by the Investigator in consultation with the Medical Monitor based on the clinical evaluation of the subject.

6.5 Pharmacokinetics

Blood samples for PK analysis of tapinarof concentration will be collected at a subset of sites in a subset of subjects at timepoints indicated in the Schedule of Assessments ([Table 1](#)) and Section 7. The actual date and time of each blood sample collection will be recorded as well as the date and time of the last dose of study drug prior to sample collection. Collection, processing, storage, and shipping procedures are provided in the Study Reference Manual or the Laboratory Manual.

Concentrations of tapinarof will be determined in plasma samples using a validated bioanalytical method. Raw data will be archived at the bioanalytical site.

Informed consent/assent for collection of PK samples will be required.

6.6 Virtual Assessments

In the event that a subject cannot attend their regularly scheduled study visits in person due to a COVID-19-like situation necessitating a limit on in-person contact, the Investigator may perform safety and efficacy assessments by phone or video. Source documentation should note if the visit was performed by phone or by video. The Investigator may use the technology platform that is currently available to them. Suggested platforms include Apple FaceTime, Zoom for Healthcare, Facebook Messenger video chat, Microsoft Teams, Google Hangouts video, and Skype. Additional details of the visit should be included in source documentation, as detailed in the Study Reference Manual.

If the subject can only be contacted by phone, the following should be assessed or performed:

- AEs
- Concomitant Medications
- Reminder to complete diary
- Instruction not to discard empty tubes of study drug

If the subject has video capabilities, the following items should be assessed or performed:

- AEs
- Concomitant Medications
- vIGA-AD™ assessment (excluding subject's scalp)

- %BSA affected calculation (excluding subject's scalp)
- EASI assessment (excluding subject's scalp)
- Investigator-assessed LTS
- Subject (or caregiver)-assessed LTS
- Application of study drug by the subject
- Completion of the PP-NRS (the subject or caregiver [as applicable] can verbally indicate the answer which the study coordinator will document in the source document)
- Reminder to complete diary
- Instruction not to discard empty tubes of study drug

The reason that assessments cannot be completed during a virtual assessment (i.e., labs, vital signs, physical exams, etc.) must be noted (e.g., COVID-19) and the missed assessments will be recorded as protocol deviations.

7 Timing of Procedures and Assessments

This section lists the procedures and assessment to be performed at scheduled timepoints during the study as outlined in the Schedule of Assessments (Table 1). Information on study procedures and assessments is provided in Section 6.

- Any change in timing or any addition of a timepoint(s) for any planned study assessment must be documented in a “Note to File,” which is approved by the relevant Sponsor study team member and then archived in the study Sponsor and site study files; this will NOT constitute a protocol amendment.
- The IRB/IEC will be informed of any safety issues that require alteration of the safety monitoring or amendment of the ICF.

NOTE: Assessments and procedures should be performed pre-dose on clinic visit days except for LTS at Weeks 1, 2 and 4.

7.1 Visit 1; Screening Period (Day -30 to Day -1)

After the subject has signed the consent/assent form, potential study subjects will undergo Screening procedures and assessments to confirm eligibility to participate in the study. Screening assessments will include the following:

- Demography recording
- Fitzpatrick skin type
- Medical history recording (including all medications administered up to 30 days prior to screening, and all systemic [oral and injectable] medications used by the subject for the treatment of AD prior to 30 days before Screening)
- Serum pregnancy test (females of child-bearing potential)
- Brief physical examination (including height and weight, body mass index will be calculated in the CRF)
- Vital signs measurements
- Blood sample collection for clinical laboratory tests (serum chemistry, hematology, diagnostic tests)
- Urinalysis
- AE recording (from the time the ICF is signed)
- Concomitant medication recording
- vIGA-AD™ score (excluding subject’s scalp)
- %BSA affected calculation (excluding subject’s scalp)
- EASI (excluding subject’s scalp)

To determine subject eligibility at Screening, a single repeat of tests or procedures may be allowed at the discretion of the Investigator. The Medical Monitor should be consulted if needed.

7.2 Visit 2; Baseline (Day 1)

On Day 1, subjects will be reassessed to confirm continued eligibility to participate in the study. All subjects who continue to meet study eligibility criteria will be randomized to treatment.

The following additional procedures and assessments will be performed at the Baseline Visit:

- Changes to medical history will be recorded
- Urine pregnancy test (females of child-bearing potential)
- Brief physical examination
- Vital signs measurement
- ECG recording (at a subset of study sites only)
- Blood sample collection for clinical laboratory tests (serum chemistry, hematology, diagnostic tests)

NOTE: Blood sample collection for clinical laboratory tests is not required at the Baseline Visit if it has been \leq 14 days since samples were collected at Screening and the results of those clinical laboratory tests were not clinically significant.

- Urinalysis

NOTE: Urine sample collection for urinalysis is not required at the Baseline Visit if it has been \leq 14 days since samples were collected at Screening and the results of those analyses were not clinically significant.

- Photography of a representative area of the subject's disease area (at a subset of study sites only)
- AE recording
- Concomitant medication recording
- vIGA-AD™ score (excluding subject's scalp)
- %BSA affected calculation (excluding subject's scalp)
- EASI (excluding subject's scalp)
- Investigator-assessed LTS (pre-dose)
- [REDACTED]
- [REDACTED]
- PP-NRS
- [REDACTED]
- [REDACTED]
- Subject (or caregiver)-assessed LTS (pre-dose)
- Dispense diary (subjects or their caregivers will be instructed on how and when to complete diary)
- Subject randomized to study treatment
- Dispense study drug
- Instruction on how to apply study drug
- Study drug application under supervision

7.3 Visit 3; Week 1 (Day 8 ±2 Days)

The following procedures and assessments will be performed at Visit 3:

- Vital signs
- vIGA-AD™ score (excluding subject's scalp)
- %BSA affected calculation (excluding subject's scalp)
- EASI (excluding subject's scalp)
- [REDACTED]
- [REDACTED]
- PP-NRS
- [REDACTED]
- [REDACTED]
- AE recording
- Concomitant medication recording
- Collect and review subject diaries for treatment compliance
- Dispense subject diaries
- Collect and dispense study drug
- Review instructions on how to apply study drug
- Study drug application under supervision
- Investigator-assessed LTS (post-dose)
- Subject (or caregiver)-assessed LTS (post-dose)

7.4 Visit 4; Week 2 (Day 15 ±2 Days)

The following procedures and assessments will be performed at Visit 4:

- Vital signs measurement
- Photography of a representative area of the subject's disease area (at a subset of study sites only)
- AE recording
- Concomitant medication recording
- vIGA-AD™ score (excluding subject's scalp)
- %BSA affected calculation (excluding subject's scalp)
- EASI (excluding subject's scalp)
- [REDACTED]
- [REDACTED]
- PP-NRS
- [REDACTED]
- [REDACTED]
- Collect and review subject diaries for treatment compliance

- Dispense subject diaries
- Collect and dispense study drug
- Review instructions on how to apply study drug
- Study drug application under supervision
- Investigator-assessed LTS (post-dose)
- Subject (or caregiver)-assessed LTS (post-dose)

7.5 Visit 5; Week 4 (Day 29 ±2 Days)

The following procedures and assessments will be performed at Visit 5:

- Urine pregnancy test (females of child-bearing potential)
- Brief physical examination
- Vital signs measurement
- ECG recording (at a subset of study sites only)
- Blood sample collection for clinical laboratory tests (serum chemistry, hematology, diagnostic tests)
- Urinalysis
- Blood sample collection for PK analysis (at a subset of study sites only)
- Photography of a representative area of the subject's disease area (at a subset of study sites only)
- AE recording
- Concomitant medication recording
- vIGA-AD™ score (excluding subject's scalp)
- %BSA affected calculation (excluding subject's scalp)
- EASI (excluding subject's scalp)
- [REDACTED]
- [REDACTED]
- PP-NRS
- [REDACTED]
- [REDACTED]
- Collect and review subject diaries for treatment compliance
- Dispense subject diaries
- Collect and dispense study drug
- Review instructions on how to apply study drug
- Study drug application under supervision
- Investigator-assessed LTS (post-dose)
- Subject (or caregiver)-assessed LTS (post-dose)

7.6 Visit 6; Week 8 (Day 57 ±2 Days)

The following procedures and assessments will be performed at Visit 6:

- Urine pregnancy test (females of child-bearing potential)
- Brief physical examination
- Vital signs measurement
- Blood sample collection for clinical laboratory tests (serum chemistry, hematology, diagnostic tests)
- Urinalysis
- Blood sample collection for PK analysis (at a subset of study sites only)
- ECG recording (at a subset of study sites only)
- Photography of a representative area of the subject's disease area (at a subset of study sites only)
- vIGA-AD™ score (excluding subject's scalp)
- %BSA affected calculation (excluding subject's scalp)
- EASI (excluding subject's scalp)
- [REDACTED]
- [REDACTED]
- PP-NRS
- [REDACTED]
- [REDACTED]
- Investigator-assessed LTS
- Subject (or caregiver)-assessed LTS
- AE recording
- Concomitant medication recording
- Collect subject diaries
- Review subject diaries for treatment compliance
- Collect study drug
- Enrollment in OL-LTE study (optional)

7.7 Phone Contact at Weeks 3 (Day 22 ±2 Days) and 6 (Day 43 ±2 Days)

Subjects or their caregivers will be contacted by phone at Weeks 3 and 6 to review study drug application instructions and to record AEs and concomitant medication use. Subjects should be reminded to complete their daily diary and bring it with them to the next clinic visit.

7.8 Follow-Up Visit 7; Week 9 (Day 64 ±2 Days)

Subjects who complete Visit 6/Week 8 but do not enroll in the OL-LTE study will return to the study site at Week 9 to complete Follow-Up assessments as follows:

- Brief physical examination

- Vital signs measurement
- If needed, blood sample collection for clinical laboratory tests
- If needed, urinalysis
- vIGA-AD™ score (excluding subject's scalp)
- %BSA affected calculation (excluding subject's scalp)
- EASI (excluding subject's scalp)
- [REDACTED]
- [REDACTED]
- PP-NRS
- [REDACTED]
- [REDACTED]
- AE recording
- Concomitant medication recording

7.9 Early Termination Visit

Subjects who withdraw early from the study will be asked to return to the study site to complete Early Termination assessments as follows:

- Urine pregnancy test (females of child-bearing potential)
- Brief physical examination
- Vital signs measurement
- Blood sample collection for clinical laboratory tests
- Urinalysis
- ECG recording (at a subset of study sites only)
- vIGA-AD™ score (excluding subject's scalp)
- %BSA affected calculation (excluding subject's scalp)
- EASI (excluding subject's scalp)
- [REDACTED]
- [REDACTED]
- PP-NRS
- [REDACTED]
- [REDACTED]
- Investigator-assessed LTS
- Subject-assessed LTS
- AE recording
- Concomitant medication recording
- Collect subject diaries

- Review subject diaries for treatment compliance
- Collect study drug

7.10 Unscheduled Visit

Subjects may have an unscheduled visit for AE follow-up, study drug dispensation, make-up for a missed visit, or other reason. The following assessments may be performed:

- Urine pregnancy test (females of child-bearing potential)
- Brief physical examination
- Vital signs measurement
- Blood sample collection for clinical laboratory tests (serum chemistry, hematology, diagnostic tests)
- Urinalysis
- ECG recording (at a subset of study sites only)
- vIGA-AD™ score (excluding subject's scalp)
- %BSA affected calculation (excluding subject's scalp)
- EASI (excluding subject's scalp)
- Investigator-assessed LTS
- Subject (or caregiver)-assessed LTS
- PP-NRS
- AE recording
- Concomitant medication recording
- Dispense and/or collect subject diaries
- Review subject diaries for treatment compliance
- Dispense and/or collect study drug
- Review instructions on how to apply study drug

7.11 End of Study

The end of study is defined as when the last active subject has completed the Week 9 Follow-up Visit which is 1 week after the end of treatment (if subject does not enroll in the OL-LTE study) OR the last active subject has completed the 8 weeks of treatment in this study (if subject is eligible and enrolls in the OL-LTE study).

8 Safety Monitoring and Reporting

8.1 Adverse Events, Serious Adverse Events, and Adverse Events of Special Interest

The Investigator or site staff is responsible for detecting, documenting, and reporting events that meet the definition of an AE, SAE, or AESIs. At each visit/contact, subjects should be questioned in a general way so as not to introduce bias in detecting AEs and/or SAEs. Open-ended and non-leading verbal questioning of the subject is the preferred method to inquire about AE occurrence.

Investigators are not obligated to actively seek AEs or SAEs in former study subjects. However, if the Investigator learns of any SAE, including a death, at any time after a subject has been discharged from the study, and he/she considers the event reasonably related to the study drug or study participation, the Investigator should promptly notify the Sponsor.

A narrative will be written and included in the Clinical Study Report for all SAEs and AESIs, and for all AEs that lead to study discontinuation.

8.1.1 Definition of Adverse Events

An AE is any untoward medical occurrence in a subject temporally associated with the use of a medicinal product, whether considered causally related or not related to the medicinal product.

An AE can therefore be any unfavorable and unintended sign (including an abnormal laboratory finding), symptom, or disease (new or exacerbated) temporally associated with the use of a medicinal product.

Events meeting the definition of an AE include:

- Any abnormal laboratory test results (hematology, clinical chemistry) or other safety assessments (e.g., vital signs measurements), including those that worsen from Baseline, and felt to be clinically significant in the medical and scientific judgment of the Investigator
- Exacerbation of a chronic or intermittent pre-existing condition (e.g., plaque psoriasis) including either an increase in frequency and/or intensity of the condition
- For skin-related AEs, it should be noted whether or not the event is in the area of active application of study drug, and/or if spreading beyond the application site.
- New conditions detected or diagnosed after study drug administration even though it may have been present prior to the start of the study
- Signs, symptoms, or the clinical sequelae of a suspected interaction
- Signs, symptoms, or the clinical sequelae of a suspected overdose of either study drug or a concomitant medication (overdose per se will not be reported as an AE/SAE)
- "Lack of efficacy" or "failure of expected pharmacological action" per se will not be reported as an AE or SAE. Such instances will be captured in the efficacy assessments. However, the signs, symptoms, and/or clinical sequelae resulting from lack of efficacy will be reported as AE or SAE if they fulfill the definition of an AE or SAE.

Events that **do not** meet the definition of an AE include:

- Any clinically significant abnormal laboratory findings or other abnormal safety assessments that are associated with the underlying disease, unless judged by the Investigator to be more severe than expected for the subject's condition

- The disease/disorder being studied or expected progression, signs, or symptoms of the disease/disorder being studied, unless more severe than expected for the subject's condition
- Medical or surgical procedure (e.g., endoscopy, appendectomy); the condition that leads to the procedure is an AE
- Situations where an untoward medical occurrence did not occur (social and/or convenience admission to a hospital)
- Anticipated day-to-day fluctuations of pre-existing disease(s) or condition(s) present or detected at the start of the study that do not worsen

8.1.2 Definition of Serious Adverse Event

If an event is not an AE per Section 8.1.1, then it cannot be an SAE even if serious conditions are met (e.g., hospitalization for signs/symptoms of the disease under study, death due to progression of disease, etc.).

An SAE is any untoward medical occurrence that, at any dose:

- Results in death
- Is life-threatening
 - The term “life threatening” refers to an event in which the subject was at risk of death at the time of the event. It does not refer to an event, which hypothetically might have caused death, if it were more severe.
- Requires hospitalization or prolongation of existing hospitalization
 - In general, signifies that the subject has been detained (usually involving at least an overnight stay) at the hospital or emergency ward for observation and/or treatment that would not have been appropriate in the physician's office or outpatient setting. Complications that occur during hospitalization are AEs. If a complication prolongs hospitalization or fulfills any other serious criteria, the event is serious. When in doubt as to whether “hospitalization” occurred or was necessary, the AE should be considered serious.
 - Hospitalization for elective treatment of a pre-existing condition that did not worsen from Baseline is not considered an AE.
- Results in disability/incapacity: a substantial disruption of a person's ability to conduct normal life functions.
 - This definition is not intended to include experiences of relatively minor medical significance such as uncomplicated headache, nausea, vomiting, diarrhea, influenza, and accidental trauma (e.g., sprained ankle) which may interfere or prevent everyday life functions but do not constitute a substantial disruption.
- Results in a congenital anomaly/birth defect

Medical or scientific judgment should be exercised in deciding whether reporting is appropriate in other situations, such as important medical events that may not be immediately life-threatening or result in death or hospitalization but may jeopardize the subject or may require medical or surgical intervention to prevent one of the other outcomes listed in the above definition. These should also be considered serious. Examples of such events are invasive or malignant cancers, intensive treatment in an emergency room or at home for

allergic bronchospasm, blood dyscrasias, or convulsions that do not result in hospitalization, or development of drug dependency or drug abuse.

8.1.3 Adverse Events of Special Interest

In prior clinical studies, contact dermatitis, folliculitis, and headache have been identified as AEs of particular clinical importance and will be reported as AESIs in this study whether or not the AE is considered related to study drug.

In each case study drug may be continued or discontinued, based on Investigator judgment, and may be restarted when the event resolves. In addition, the following information must be collected for each of these AESIs:

Contact Dermatitis

The study site should collect location, duration, size, associated symptoms (itching, burning, pain), severity (mild, moderate, severe), time to onset, and photograph the affected site (if possible). If the subject or caregiver contacts the study site to report significant skin irritation at or near the site of study drug application between study visits, the subject should be brought in for an unscheduled visit, if possible.

Headache

The study site should collect duration, severity (mild, moderate, severe), time to onset, and location (e.g., frontal, temporal, occipital, diffuse).

Follicular Event

The study site should collect the location, duration, size, associated signs and symptoms (itching, burning, pain, erythema), severity (mild, moderate, severe), describe morphology [scale (keratotic/cornified) or no scale (non-keratotic/non-cornified)], time to onset, and photograph the affected site (if possible). Additional information regarding management of folliculitis is provided in Section 8.2.1.2.4.

In particular, the term 'folliculitis' may not correctly describe the morphology of the observed local follicular events as these appear to be more consistent with a keratoses pilaris-like follicular based papule. Tapinarof upregulates components of the stratum corneum, including involucrin, hornerin, and filaggrin and increased cornification at, and subsequent mechanical occlusion of, the follicular ostia has been suggested to be a potentially on target mechanism by which these lesions may develop in some individuals treated with tapinarof cream. Additional morphologic description will help to more fully and appropriately characterize these follicular events.

Possible descriptors include, but are not limited to:

- Folliculitis
 - Non-inflammatory
 - Inflammatory
- Milia
 - Non-inflammatory
 - Inflammatory
- Keratosis pilaris

- Non-inflammatory
- Inflammatory

Additional AESIs may be identified during the evaluation of safety data for the Clinical Study Report.

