4.6.1 Reasons for Withdrawal from the Study

Study drug will be discontinued and the subject withdrawn from the study for any of the following reasons:

- Subject has an AE that is considered to be related to study drug or procedures AND is severe enough to warrant treatment discontinuation, as determined by the Investigator (Section 8.1).
- Pregnancy
- Any Grade 3 or 4 AE, based on Cancer Institute Common Terminology Criteria for Adverse Events (CTCAE) criteria, considered causally related to study drug (Section 8.2.2)

Study drug may be discontinued and the subject withdrawn from the study for any of the following reasons:

- Subject requires concurrent prohibited medication during the study (Section 5.6.2). Nonmedicated emollients that do not contain salicylic acid may be used on nonlesional skin but the subject (or caregiver) should wait at least 30 minutes after applying study drug before applying nonmedicated emollients; emollients should not be applied to lesional skin during treatment. The same emollient should be used throughout the subject's participation in the study.

NOTE: If, in the opinion of the Investigator and the study Medical Monitor, such medication will not interfere with the conduct or interpretation of the study or compromise the safety of the subject, then the subject may continue to receive study drug. If the subject is permanently discontinued from study drug, they may remain in the study for safety assessments as needed, at the discretion of the Investigator and Medical Monitor, but they are not eligible to enroll in the OL-LTE.

- Subject noncompliance
- Investigator noncompliance
- Discontinuation of the study at the request of the Sponsor, regulatory agency, or an Institutional Review Board (IRB)/Independent Ethics Committee (IEC).

If a subject meets a withdrawal criterion during treatment, an Early Termination visit will be required (Section 7.9).

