8.2 Classification of Adverse Events

8.2.1 Assigning Severity Rating for Adverse Events

8.2.1.1 Criteria for Determining Adverse Event Severity

The Investigator will make an assessment of the severity of each AE and SAE according to the National Cancer Institute CTCAE, v. 5.0, 2017. For terms not specified with the CTCAE, the criteria in Table 5 should be used to determine the grade severity.

Table 5: Criteria for Determining the Grade/Severity of Adverse Event Terms Not Specified by the National Cancer Institute CTCAE

Grade	Criteria
1	Mild; asymptomatic or mild symptoms, clinical or diagnostic observations only; intervention not indicated
2	Moderate; minimal, local, or noninvasive intervention indicated; limiting age-appropriate instrumental activities of daily living ^a
3	Severe or medically significant but not immediately life-threatening; hospitalization or prolongation of hospitalization indicated; disabling; limiting self-care activities of daily living ^b
4	Life threatening consequences; urgent intervention indicated
5	Death related to adverse event

a. Instrumental activities of daily living refer to preparing meals, shopping for groceries or clothes, using the telephone, managing money, etc.

b. Self-care activities of daily living refer to bathing, dressing and undressing, feeding self, using the toilet, taking medications, and not bedridden.

CTCAE = Common Terminology Criteria for Adverse Events.

AE severity should be recorded in the appropriate section of the AE CRF and in the subject's source documents.

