8.2.1.2 Toxicity Management Criteria

8.2.1.2.1 Grade 1 or Grade 2 Adverse Event

Subjects who develop a Grade 1 or Grade 2 AE may continue investigational product at the discretion of the Investigator. Subjects who choose to withdraw from study due to a Grade 1 or 2 AE should have study withdrawal/early termination evaluations completed.

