8.2.1.2.2 Grade 3 Adverse Event

Subjects who develop a Grade 3 AE should be managed as follows:

- If the Investigator has compelling evidence that the Grade 3 AE has not been caused by investigational product, then dosing may continue after discussion with the Medical Monitor.
- Subjects who develop a Grade 3 AE that the Investigator considers related to investigational product should have the investigational product discontinued. Subjects experiencing Grade 3 AEs requiring permanent discontinuation of investigational product should be followed weekly until resolution or stability of the AE and encouraged to have withdrawal study evaluations completed.

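### Protocol 8.1.3 lets sites continue or restart study drug after a related Grade 3 or 4 event of special interest, where 4.6.1 requires discontinuation and withdrawal

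*Protocol*

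**What the plan says.** Protocol 8.1.3 names contact dermatitis, folliculitis (follicular events) and headache as adverse events of special interest (AESIs), whether or not they are judged related to study drug. Its dosing rule is: "In each case study drug may be continued or discontinued, based on Investigator judgment, and may be restarted when the event resolves". The section then lists the data to collect. For headache: "The study site should collect duration, severity (mild, moderate, severe), time to onset, and location". The same three severity levels are listed for contact dermatitis and follicular events.

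Protocol 4.6.1 gives the mandatory rule: "Study drug will be discontinued and the subject withdrawn from the study for any of the following reasons". One of the listed reasons is: "Any Grade 3 or 4 AE, based on Cancer Institute Common Terminology Criteria for Adverse Events (CTCAE) criteria, considered causally related to study drug".

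Protocol 8.2.1.2 sets toxicity management by grade:

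- **Grade 1 or 2 (8.2.1.2.1):** "Subjects who develop a Grade 1 or Grade 2 AE may continue investigational product at the discretion of the Investigator".
- **Grade 3, related (8.2.1.2.2):** "Subjects who develop a Grade 3 AE that the Investigator considers related to investigational product should have the investigational product discontinued".
- **Grade 3, not related (8.2.1.2.2):** the Investigator needs "compelling evidence that the Grade 3 AE has not been caused by investigational product, then dosing may continue after discussion with the Medical Monitor".
- **Grade 4 (8.2.1.2.3):** permanent discontinuation, with no reference to causality.

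**The concern.** 8.1.3 applies to every AESI, and its severity list shows that severe events were in view. Read literally, it lets the Investigator keep a subject on drug, or restart drug, after a severe AESI judged related. 4.6.1 removes that choice for any related Grade 3 or 4 event. A withdrawn subject cannot be restarted, so the 8.1.3 permission and the 4.6.1 rule cannot both be used for the same event.

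What is at stake is subject safety. The protocol itself singles out these three events as clinically important. Adults are capped at 20% of enrolment (Protocol 4.1), so at least about 80% of subjects will be under 18. The mandatory rule exists to prevent re-exposure after a severe related reaction, and a site could read 8.1.3 as permission for it.

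There is also a small consistency issue. Stopping treatment because of an adverse event counts as treatment failure in the primary estimand (Protocol 10.4.2.1, SAP 11.1). Sites that resolve the conflict differently would therefore classify similar subjects differently.

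**Working it through.** The finding itself is textual. Taking each type of AESI in turn:

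| AESI | 8.1.3 | 4.6.1, Grade 3/4 item | 8.2.1.2 | Consistent? |
|---|---|---|---|---|
| Grade 1–2 | Continue, stop or restart, Investigator's choice | Not triggered | Continue at Investigator's discretion | Yes |
| Grade 3, not related | Same | Not triggered | Continue only with compelling evidence and after Medical Monitor discussion | 8.1.3 omits two conditions |
| Grade 3, related | Same | Stop drug and withdraw | Should stop | **No** |
| Grade 4, not related | Same | Not triggered | Should stop permanently | 8.1.3 out of line with 8.2.1.2.3 |
| Grade 4, related | Same | Stop drug and withdraw | Should stop permanently | **No** |

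**Can an AESI reach Grade 3?** Protocol 8.2.1.1 grades every adverse event by CTCAE, with Table 5 for terms that CTCAE does not specify. Table 5 describes Grade 3 as "Severe or medically significant but not immediately life-threatening", which matches the top level of the 8.1.3 severity list. Whether CTCAE or Table 5 applies to a given AESI term cannot be settled from these documents. Either way the event receives a grade, and 8.1.3 excludes none.

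**Does anything reconcile the two sections?**

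- 8.1.3 does not refer to 4.6.1 or to the Grade 3 and 4 rules. Its only management cross-reference is to 8.2.1.2.4, which offers temporary interruption for symptomatic folliculitis and also sets no grade limit.
- 4.6.1 has no AESI exception. Its first item leaves room for Investigator judgment on related events, but the separate Grade 3/4 item does not. Its note on continuing drug concerns prohibited medication.
- 8.2.1.2.2 mentions Grade 3 events that need permanent discontinuation, which might suggest that some stops could be temporary. 4.6.1 would still require withdrawal.
- Protocol Section 6 rules out waivers and exemptions except for immediate safety concerns.

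**How many subjects, and what effect on the result?** The documents give no Grade 3–4 AESI rate. Assume 0.5% to 2% of the 267 planned tapinarof subjects (Protocol 10.2):

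- 267 × 0.005 = 1.3 subjects
- 267 × 0.02 = 5.3 subjects

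Suppose all of them were restarted and responded at the planned 45%, when under 4.6.1 all would count as failures. The tapinarof response rate would differ by:

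- 0.5% × 0.45 = 0.2 percentage points
- 2% × 0.45 = 0.9 percentage points

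The planned difference is 45% − 25% = 20 points.

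**The case against.** The strongest reply is that there is no true contradiction. 8.1.3 is permissive and broad; 4.6.1 is mandatory and narrow. On an ordinary reading, a general discretion operates inside a specific stopping rule, and a site that stops drug complies with both. Placement supports this: 8.1.3 is mainly about definitions and data collection, and toxicity management sits in 8.2.1.2. That reading is reasonable and probably what the sponsor intends, but no visible text states it. A site could equally treat the AESI sentence as the specific rule and 4.6.1 as the general one, which is the less safe choice.

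Several narrower points stand in part:

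- The 8.1.3 severity list stops at severe, and nothing in the documents describes a Grade 4 AESI. The practical case is therefore mostly a related Grade 3 event. The wording still excludes no grade.
- Table 5 applies only to terms that CTCAE does not specify, so it cannot alone show how a given AESI would be graded. The overlap does not depend on it, because every event is graded one way or the other.
- Section 5.1.6 and part of 1.3 are redacted, so the absence of a reconciling sentence can be confirmed only for the visible text.
- 8.2.1.2.2 and 8.2.1.2.3 are worded as recommendations, and 8.2.1.2.5 asks for Medical Monitor notification of severe signs that put a subject at risk. These soften the secondary comparisons but leave 4.6.1 untouched.
- Such events should be rare. 8.2.1.2.4 says most folliculitis is mild or moderate; it makes no such statement about contact dermatitis or headache.

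**Conclusion.** The concern holds. For a related Grade 3 or 4 AESI, 8.1.3 permits what 4.6.1 forbids, and the visible documents give no order of precedence. The 4.6.1 conflict is confined to those events. Grade 1–2 events are unaffected, and for unrelated Grade 3 or 4 events the mismatch is only with 8.2.1.2.

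The instruction is wrong as written on a patient-safety matter, and the severity is low. About 1 to 5 tapinarof subjects would be involved under the assumed rates, which have no support in the documents. The 0.2 to 0.9 point effect is the extreme case in which every such subject restarts and responds at the planned rate. No material effect on the primary result is claimed.

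**What to change.** Open the dosing sentence in 8.1.3 with the clause *Subject to Sections 4.6.1 and 8.2.1.2*, and leave the rest as it is. The mandatory withdrawal rule and the grade-specific rules then govern, and Investigator discretion for Grade 1–2 events is preserved. Tell sites by memo.

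If the sponsor does intend an exception for AESIs, it must instead be written into 4.6.1 and 8.2.1.2, where the stopping rules sit.

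The cost is one clause in 8.1.3 and a site memo. No analysis or sample-size change is needed.
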